10.1 Collection of Safety Information

Adverse Event (AE) is defined as any new untoward medical occurrence or worsening of a pre-existing medical condition in a patient administered a medicinal product in a clinical investigation and which does not necessarily have a causal relationship with this treatment. An AE can therefore be any unfavorable and unintended sign (including an abnormal laboratory finding, for example), symptom, or disease temporally associated with the use of a product (investigational or marketed), whether or not considered related to the product (investigational or marketed). Abnormal laboratory values or test results constitute adverse events only if they induce clinical signs and symptoms, are considered clinically significant, or require therapy.

Following written consent to participate in the study, all serious AEs should be collected on a patient. The collection of non-serious AE information should begin at initiation of therapy.

All identified AEs must be recorded and described on the appropriate page of the Case Report Form (CRF). If known, the diagnosis of the underlying illness or disorder should be recorded, rather than individual symptoms. The following information should be documented for all AEs: date of onset and resolution, severity of the event; the investigator's opinion of the relationship to investigational product (see definitions below); treatment required for the AE; cause of the event (if known); and information regarding resolution/outcome.

Severity

CTCAE term (AE description) and grade: The descriptions and grading scales found in the revised NCI Common Terminology Criteria for Adverse Events (CTCAE) Version 4.0 will be utilized for AE reporting. A copy of the CTCAE Version 4.0 can be downloaded from the CTEP web site (<http://ctep.cancer.gov>).

All appropriate treatment areas should have access to a copy of the CTEP CTCAE Version 4.0 (see Appendix E).

Attribution

The following categories and definitions of causal relationship or attribution to study drug should be used to assess Adverse Events:

- **Definite:** There is a reasonable causal relationship between the study drug and the event. The event responds to withdrawal of study drug (dechallenge) and recurs with rechallenge, if clinically feasible.
- **Probable:** There is a reasonable causal relationship between the study drug and the event. The event responds to dechallenge. Rechallenge is not required.

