- **Possible:** There is a reasonable causal relationship between the study drug and the event. Dechallenge information is lacking or unclear.
- **Unlikely:** There is doubtful causal relationship between the study drug and the event.

- Unrelated: There is clearly not a causal relationship between the study drug and the event or there is a causal relationship between another drug, concurrent disease, or circumstances and the event.

Categories 'Definite', 'probable' and 'possible' are considered study drug related. Categories 'not likely' and 'not related' are considered not study drug-related.

The development of a new cancer should be regarded as an AE. New cancers are those that are not the primary reason for administration of study treatment and have been identified after inclusion of the patient into the clinical study.

AEs related to fulvestrant and/or everolimus/placebo will be followed for 30 days after the last dose of study therapy (fulvestrant and/or everolimus/placebo) until ≤ grade 1 or stabilization, and reported as SAEs if they become serious. Serious adverse events >30 days after last dose of fulvestrant and/or everolimus/placebo are not reported unless the event may be related to everolimus/placebo.

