10.3 Reporting of Second Primary Cancers

New cancers are those that are not the primary reason for administration of study treatment and have been identified after inclusion of the patient into the clinical study.

All cases of new primary cancers that occur during or after protocol treatment must be reported to PrECOG within 30 days of diagnosis, regardless of relationship to protocol treatment. Secondary primary malignancies should also be reported as a SAE. This form is not for use for reporting recurrence or development of metastatic disease. A copy of the pathology report, if applicable, should be sent, if available.

Note: Once data regarding survival and remission status are no longer required by the protocol, no follow-up data should be submitted, including the PrECOG Second Primary Form.

11 Administrative

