### 6.1. Adverse Events

Adverse Event (AE) is defined as any new untoward medical occurrence or worsening of a pre-existing medical condition in a subject administered a medicinal product in a clinical investigation and which does not necessarily have a causal relationship with this treatment. An AE can therefore be any unfavorable and unintended sign (including an abnormal laboratory finding, for example), symptom, or disease temporally associated with the use of a product (investigational or marketed), whether or not considered related to the product (investigational or marketed).

Treatment-emergent AEs: any adverse event starting on or after the first treatment dose.

AE Severity:

**CTCAE term (AE description) and grade:** The descriptions and grading scales found in the revised NCI Common Terminology Criteria for Adverse Events (CTCAE) Version 4.0 will be utilized for AE reporting. A copy of the CTCAE Version 4.0 can be downloaded from the CTEP web site (<http://ctep.cancer.gov>).

All appropriate treatment areas should have access to a copy of the CTEP CTCAE Version 4.0 (see Protocol Appendix E)

AE Attribution (Relationship)

The following categories and definitions of causal relationship or attribution to study drug should be used to assess Adverse Events:

- Definite: There is a reasonable causal relationship between the study drug and the event. The event responds to withdrawal of study drug (dechallenge) and recurs with rechallenge, if clinically feasible.
- Probable: There is a reasonable causal relationship between the study drug and the event. The event responds to dechallenge. Rechallenge is not required.
- Possible: There is a reasonable causal relationship between the study drug and the event. Dechallenge information is lacking or unclear.
- Unlikely: There is doubtful causal relationship between the study drug and the event.
- Unrelated: There is clearly not a causal relationship between the study drug and the event or there is a causal relationship between another drug, concurrent disease, or circumstances and the event.

Categories 'Definite', 'probable' and 'possible' are considered study drug related. Categories 'not likely' and 'not related' are considered not study drug-related.

The development of a new cancer is to be regarded as an AE. New cancers are those that are not the primary reason for administration of study treatment and have been identified after inclusion of the subject into the clinical study.

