## **7.8. Safety Analysis**

### **7.8.1. Adverse Events**

Adverse events (AEs) will be graded using CTC Version 4, coded using MedDRA dictionary version 16.0, and flagged as treatment emergent if start date of the adverse event is on or after Cycle 1 Day 1 dosing. For adverse events with partial start date (i.e., with only month and year are recorded), the following imputation rule will be applied: 15th of the month or first dose date, whichever comes later.

All AEs and treatment-related AEs will be summarized for all treated subjects by toxicity grade and by treatment arm.

AEs with relationship reported as 'Definite', 'probable' and 'possible' are considered study drug related. AEs with relationship reported 'not likely' and 'not related' are considered not study drug-related. AEs with missing relationship will be considered study drug related.

The following by subject data listings will be prepared: subjects with serious adverse events, subjects with Grade 5 adverse events, and subjects with second primary cancer.

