## 11. APPENDIX 1: LIST OF TABLES, LISTINGS AND FIGURES REQUESTED FOR PUBLICATION

*The following list of required TLFs was provided by PrECOG on 24 May 2013.*

PrE0102 Tables, Listings, Figures  
5/24/13

Table (1): Accrual by Institution

Table (2): Case Status (by arm and total):

Number Enrolled  
Number Ineligible  
Number Withdrawn before Treatment  
Eligible and Treated

Listing (1): Reasons ineligible

Listing (2): Reasons for not starting treatment

Table (3) of Stratification Factors (by arm and total)

Cross-tab (4) of Stratification Factors and Corresponding data from CRF (by arm and total)

Table (5): Subject Characteristics at Study Entry (by arm and total)

Table (6): Number Cycles of Treatment Received by Reason off Treatment (by arm)

Table (7): Dosing: Median and range dose during induction and continuation (by arm and agent)

Toxicity Tables (include all subjects receiving at least 1 dose of study drug/placebo. Count each subject once at the highest grade):

(8) All events, grade 1 to 5, regardless of attribution, by arm and grade

Count

Percent

(9) Treatment-related events, grade 1 to 5, by arm and grade

Count

Percent

Above 2 tables should use CTCAE terminology if possible

(10, 11) Same 2 tables, by System Organ Class rather than individual event

Listing (3) of Serious Adverse Events

Listing (4) of Subjects with Grade 5 Adverse Events

Table (12) of Best Overall Response, by response category and treatment arm, including unevaluable subjects as non-responders

Table (13): Objective Response rate and 90% exact binomial confidence interval, by arm, and Clinical Benefit Rate (CR+PR+SD) with 90% exact binomial confidence interval, by arm and both overall

List (5) of Subjects Unevaluable for Response, with arm and reason

Listing (6) of Second Primary Cancers

Table (14) showing PFS, TTP and OS: Median and 90% CI, or 2-year rates with 90% CI

Listing (7) of Bone Modifying Medications

Figure 1 – PFS by treatment arm

Figure 2 – OS by treatment arm

An additional listing for Bone Modifying Medication was requested via email on 11Jun2013.

For completeness, an additional table summarizing adverse events was included in TLF templates.

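### Toxicity Tables 8-11 state no event window: the treatment-emergent flag is derived but applied to no listed table and has no end date, so pre-dose and selectively collected late SAEs can be counted

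*SAP*

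**What the plan says.** **What is tabulated.** SAP 7.8.1: "All AEs and treatment-related AEs will be summarized for all treated subjects by toxicity grade and by treatment arm". SAP Appendix 1, Table 8, asks for: "All events, grade 1 to 5, regardless of attribution, by arm and grade". Table 9 is the treatment-related version, and Tables 10 and 11 repeat both by system organ class. Each subject counts once, at the highest grade. No dates are given.

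**The flag.** SAP 7.8.1 has events "flagged as treatment emergent if start date of the adverse event is on or after Cycle 1 Day 1 dosing". SAP 6.1 defines the term in the same way: "Treatment-emergent AEs: any adverse event starting on or after the first treatment dose". Neither gives a closing date. An incomplete start date becomes "15 th of the month or first dose date, whichever comes later".

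**What is collected.**
- Protocol 10.1: "Following written consent to participate in the study, all serious AEs should be collected on a patient". Non-serious AEs are collected only from the start of therapy.
- Protocol 10.1, late events: "Serious adverse events >30 days after last dose of fulvestrant and/or everolimus/placebo are not reported unless the event may be related to everolimus/placebo". Protocol 7.1.4, for the period after the Continuation Phase, names everolimus alone. Protocol 10.2.2 sends late fulvestrant-related SAEs through the commercial reporting route.
- Protocol 10.3: "All cases of new primary cancers that occur during or after protocol treatment must be reported to PrECOG within 30 days of diagnosis", whatever the relationship. Protocol 10.1 and SAP 6.1 class a new cancer as an AE.

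**Text pointing to a start at first dose.** SAP 7.2 and Protocol 6.1.1 make patients evaluable for toxicity from first treatment. They set follow-up at 30 days after the last dose, or until attributed toxicity recovers if that is longer. Protocol 7.1.2.1 starts AE assessment after the first dose.

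**The concern.** A toxicity table compares arms fairly when both arms' events are collected under one rule over one period. Here the collection rule changes twice. Before the first dose only serious events are recorded. From the first dose to 30 days after the last dose, all AEs are recorded. After that, an SAE is recorded only if someone judges that it may be related to everolimus/placebo. A table of all AEs with no dates pools the three periods.

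The two ends do different things. A pre-dose SAE cannot be a drug effect, so it only adds noise. A late SAE that is recorded because of its attribution can add bias wherever the person judging it knows the arm. At stake are the published rates of overall and grade 3-4 toxicity, which Protocol 9.2 plans to compare descriptively.

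**Working it through.** **1. The plan's own safety figures (Protocol 9.2, 65 treated per arm).**
- Widest exact 90% binomial interval over 0 to 65 events: 21.6 points, at 33 events. The plan states 22.
- Probability of at least one event at a true rate of 5%: 1 - 0.95^65 = 0.964. The plan states 96%.

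Both reproduce. The issue is which events are counted, not the precision.

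**2. Rule against collection, period by period.**

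| Event starts | Collected | Flagged treatment-emergent | In Tables 8-11, read literally |
|---|---|---|---|
| Consent to first dose | SAEs only | No, if the date is complete | Yes |
| First dose to last dose + 30 days | All AEs | Yes | Yes |
| Later | SAEs possibly related to everolimus/placebo; second cancers | Yes | Yes |

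Applying the flag as it stands would remove the first row but leave the third.

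**3. Partial dates.** When only month and year are known, the start becomes the later of the 15th and the first-dose date.
- Recorded month before the first-dose month: the 15th precedes first dose, so the event moves to the first-dose date and is flagged, although it is known to be pre-dose.
- Same month, first dose on day d: max(15, d) is never below d, so it is flagged. The true order is unknown.
- Later month: flagged, correctly.

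No event dated only by month and year can fail the flag. SAP 7.8.1 also treats a missing relationship as related, so a pre-dose SAE without an attribution could reach the treatment-related tables.

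**4. Who is unblinded by plan.** Twelve 28-day cycles are 336 days; 336/30.4375 = 11.0 months. Assume exponential PFS with the Protocol 9.1 medians:
- Placebo arm: 2^(-11.04/5.4) = 0.24, and 0.24 x 65 = about 16 patients.
- Everolimus arm: 2^(-11.04/9.2) = 0.44, and 0.44 x 65 = about 28 patients.

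These ignore dropout, so they are upper figures under the assumption. In this group, a late SAE in a placebo-arm patient can hardly be judged related to a drug that she is known not to have taken. How many late SAEs would arise is not given.

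**5. Scale of one patient.** 1/65 = 1.5 points; an assumed 1 to 3 patients gives 1.5 to 4.6 points. The common grade 3-4 events on everolimus in the everolimus-exemestane trial (Protocol 1.4.3.4) ran at 3-8%. On 65 patients that is 65 x 0.03 = 2 to 65 x 0.08 = 5, so one extra patient in a row is visible.

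**6. Pre-dose noise.** The documents give no pre-dose SAE rate. An assumed 1-3% gives 130 x 0.01 = 1.3 to 130 x 0.03 = 3.9 patients over both arms and all terms. Even if a 3% independent background fell wholly in one term, a 7-point difference (8% against 1%, the stomatitis figures in that trial) would become 0.97 x 7 = 6.8 points.

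**The case against.** The strongest reply is that a window is already implied. SAP 7.2, Protocol 6.1.1 and Protocol 7.1.2.1 all begin toxicity evaluation at first treatment, and a flag is presumably derived in order to be used. The table templates are a separate document that was not available for this review, and Appendix 1 mentions an added AE summary table that may use it. This stands in part. A reader might infer that the SAP intends to count pre-dose SAEs; the documents do not support that, and the matter is unresolved. But SAP 7.2 defines a population and a follow-up duration, not the events that Tables 8-11 count. It also fixes no closing date, because follow-up can run until recovery.

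A second reply is that the late-SAE rule names everolimus/placebo, so while patients are blinded it treats the arms alike. That stands. A reader might infer that the whole safety comparison is biased against everolimus. The text supports a tilt only where the arm is known, which by plan means patients who completed 12 cycles without progression.

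Third, second cancers might look like another source of arm-dependent counting. They are not: they are reported in both arms regardless of relationship. Nor are they collected without limit. Protocol 10.3 ends reporting when survival data are no longer required, and Protocol 7.1.5 sets follow-up at 3 years from randomization.

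Finally, each subject counts once at the highest grade, so a pre-dose SAE changes a cell only if it exceeds her on-treatment grade. The comparison also carries no test. Both points limit the size of the effect; neither supplies the missing window.

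**Conclusion.** The gap is real and modest. As written, Tables 8-11 have no stated window, and the only date rule available has no end and is not applied to them. The pre-dose part is noise that should be balanced by randomization and blinding, and it is small under any plausible rate. The late part can tilt the descriptive comparison against everolimus among patients unblinded after 12 cycles. At the protocol's medians, with exponential PFS and no dropout, that group is at most about 16 and 28 of 65. The size of the tilt cannot be derived from the documents; only the unit can, at 1.5 points per patient. The conclusion rests on the SAP text alone. If the table templates already limit events to a window with an end, only the SAP wording and the partial-date rule need correcting.

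**What to change.** Amend SAP 7.8.1 as follows.

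1. Limit Tables 8-11 to AEs that start, or worsen, from the first dose of study therapy through 30 days after the last dose of fulvestrant or everolimus/placebo. Give the treatment-emergent definition in SAP 6.1 the same end.
2. Keep second cancers that start in that window in the tables, since both documents class a new cancer as an AE.
3. Show pre-dose SAEs, SAEs after the window and later second cancers in the listings already planned (Listing 3 for SAEs, Listing 6 for second primary cancers).
4. Change the partial-date rule so that an event whose recorded month is before the month of first dose is not moved to the first-dose date. Without this, the date filter would still admit events known to be pre-dose.

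The cost is a short amendment and a date filter in the table programs. SAP 2.1 requires these sections to be agreed before database lock, so that is the time to do it. No new data are needed. The downside is that late SAEs judged related to everolimus would appear only in listings, so the report should point the reader to them.

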## **8. REPORTING CONVENTIONS**

The mean and median will be displayed to one decimal place greater than the original value and the standard deviation will be displayed to two decimal places greater than the original value. All statistical programming and analyses will be performed using SAS® Release 9.2 (SAS Institute Inc., Cary, North Carolina, USA).

The following standards will be used in the data presentation:

- Tables should be in landscape format. Output should adhere to US / International Conference on Harmonization (ICH) margins and should not require changes for European page size. A blank row will separate the header from the content of the table listing. For tables that have “n (%)", the placement should be centered below “N=xx" in the column header. Frequency tables will be center justified. Descriptive statistics will be decimal aligned.
- Percentages presented in in-text tables should be rounded to one decimal using the SAS rounding function. If "%" is part of the column heading, do not repeat the "%" sign in the body of the table. Unless specified otherwise, "%" should reflect the total population of the treatment groups. Any deviation from that should be part of the footnote. For 0 counts, leave the corresponding percentage blank.
- The heading should consist of four lines. Line 1: Sponsor identifier. Line 2: Protocol identifier. Line 3: blank line. Line 4: Table/Appendix number Table Title – Population. The title for in-text tables should begin with the Table/Appendix number.
- All data listings will be sorted by Subject Number and time point (if applicable).
- The date format for all dates is DDMMYY YYYY.

A solid line should appear both above and below the column headings of a table. A solid line should appear at the end of the table or at the bottom of each page if the table extends to more than one page. Footnotes should start after the bottom solid line.

## **9. REFERENCES**

References are provided in the protocol.

## **10. TABLES, FIGURES, AND LISTINGS**

See separate template document.

## 11. APPENDIX 1: LIST OF TABLES, LISTINGS AND FIGURES REQUESTED FOR PUBLICATION

*The following list of required TLFs was provided by PrECOG on 24 May 2013.*

PrE0102 Tables, Listings, Figures  
5/24/13

Table (1): Accrual by Institution

Table (2): Case Status (by arm and total):

Number Enrolled  
Number Ineligible  
Number Withdrawn before Treatment  
Eligible and Treated

Listing (1): Reasons ineligible

Listing (2): Reasons for not starting treatment

Table (3) of Stratification Factors (by arm and total)

Cross-tab (4) of Stratification Factors and Corresponding data from CRF (by arm and total)

Table (5): Subject Characteristics at Study Entry (by arm and total)

Table (6): Number Cycles of Treatment Received by Reason off Treatment (by arm)

Table (7): Dosing: Median and range dose during induction and continuation (by arm and agent)

Toxicity Tables (include all subjects receiving at least 1 dose of study drug/placebo. Count each subject once at the highest grade):

(8) All events, grade 1 to 5, regardless of attribution, by arm and grade

Count

Percent

(9) Treatment-related events, grade 1 to 5, by arm and grade

Count

Percent

Above 2 tables should use CTCAE terminology if possible

(10, 11) Same 2 tables, by System Organ Class rather than individual event

Listing (3) of Serious Adverse Events

Listing (4) of Subjects with Grade 5 Adverse Events

Table (12) of Best Overall Response, by response category and treatment arm, including unevaluable subjects as non-responders

Table (13): Objective Response rate and 90% exact binomial confidence interval, by arm, and Clinical Benefit Rate (CR+PR+SD) with 90% exact binomial confidence interval, by arm and both overall

List (5) of Subjects Unevaluable for Response, with arm and reason

Listing (6) of Second Primary Cancers

Table (14) showing PFS, TTP and OS: Median and 90% CI, or 2-year rates with 90% CI

Listing (7) of Bone Modifying Medications

Figure 1 – PFS by treatment arm

Figure 2 – OS by treatment arm

An additional listing for Bone Modifying Medication was requested via email on 11Jun2013.

For completeness, an additional table summarizing adverse events was included in TLF templates.

## 12. APPENDIX 2: SCHEDULED ASSESSMENTS

Procedure	Induction Phase (fulvestrant + everolimus or placebo for a maximum of 12 cycles)					End of Induction Phase <OR> End of Treatment Section 5.6 a	Continuation Phase e (until progression or unacceptable toxicity)	Follow-Up Off Therapy (every 3 months for total of 3 yrs from date of randomization)
	Pre-Study	Cycle 1 Day 1 *	Cycle 1 Day 15	Day 1 Each Subsequent Cycle *	Every 12 weeks			
Eligibility Assessment	X a							
Informed Consent	X a							
Medical History & Assessment of Baseline Signs and Symptoms	X a							
Physical Exam	X a	X b	X	X c		X		
Concomitant Meds (see Appendix C)	X a	X b	X	X c		X		
Vital Signs (Blood Pressure, Heart Rate, Temperature) and Weight	X a (includes Ht)	X b	X	X c		X		
ECOG Performance Status	X a	X b	X	X c		X		
Adverse Events Assessments		X b	X	X c		X h	X h	X h,m
Imaging Scans	X a,g				X g	X g	X g	X g,k,m
PT with INR	X a							
Urinalysis	X a							
CBC with differentials, Platelets	X a	X b	X d	X c,d		X d	X i	
Serum Creatinine, Electrolytes (K, Na, Cl, CO 2 ), Ca, BUN, Bicarbonate, Albumin, Total Protein, Phosphorus, AST (SGOT), ALT (SGPT), Alkaline Phosphatase, Total Bilirubin, Magnesium, Uric Acid.	X a	X b	X	X c		X	X i	
Fasting Glucose	X a	X b		X e	X e	X e	X i	
Fasting serum Lipid Profile (triglycerides, total cholesterol, HDL and LDL)	X a	X b		X e	X e	X e	X i	

Procedure	Induction Phase (fulvestrant + everolimus or placebo for a maximum of 12 cycles)					End of Induction Phase <OR> End of Treatment Section 5.6 a	Continuation Phase b (until progression or unacceptable toxicity)	Follow-Up Off Therapy (every 3 months for total of 3 yrs from date of randomization)
	Pre-Study	Cycle 1 Day 1*	Cycle 1 Day 15	Day 1 Each Subsequent Cycle*	Every 12 weeks			
HBV- DNA, HbsAg, HBs Ab, HBc Ab, HCV- RNA-PCR	X a,f							
HBV DNA, HCV RNA-PCR		X f		X f			X i	
Study Drug Compliance (Pill Diary)			X	X		X	X j	
PFTs with DLCO as medically indicated l								

**a:** ≤ 4 weeks of randomization; if assessments required ≤ 7 days of Cycle 1 Day 1 (C1D1), they do not need to be repeated (includes labs).

**b:** ≤ 7 days prior to the start of C1D1.

**c:** ≤ 72 hour window allowed prior to D1 of each subsequent cycle after the first cycle for scheduled therapy/tests/visits. Delay due to holidays, weekends, bad weather or other unforeseen circumstances will be permitted.

**d:** In the event of grade 3 or 4 hematologic toxicity, CBC with differential and platelet count will be obtained every 1-3 days until there is evidence of hematologic recovery.

**e:** ≤ 72 hrs prior to Cycle 2 Day 1 then approximately every 12 weeks during treatment (and more frequently as clinically indicated), and at end of treatment.

**f:** All patients should be screened for hepatitis risk factors and any past illnesses of hepatitis B and hepatitis C infection. It is highly recommended that patients positive HBV-DNA or HBsAg are treated prophylactically with an antiviral (e.g., Lamivudine) for 1-2 weeks prior to receiving study drug (see Table 5-3). The antiviral treatment should continue throughout the entire study period and for at least 4 weeks after the last dose of everolimus. Patients with viral hepatitis C risk factors should be screened for HCV RNA-PCR. Patients on antiviral prophylaxis treatment or positive HBV antibodies should be tested for HBV-DNA ≤ 7 days prior to the start of C1D1 and ≤ 72 hrs prior to D1 of each subsequent cycle to monitor for reactivation. See Table 5-4 for reactivation instructions. Patients with positive HCV RNA-PCR results at screening and/or a history of past infection (even if treated and considered 'cured') should have HCV RNA-PCR testing performed on ≤ 7 days prior to the start of C1D1 and ≤ 72 hrs prior to D1 of each subsequent cycle to monitor for flare. Everolimus must be discontinued if HCV flare is confirmed according to the guidance in Table 5-5.

**g:** Tumor measurements may be made using physical examination, CT Scans or MRI. Tumor assessments will be performed every 12 weeks, +/- week (every 3 months) with first assessment within 2 weeks prior to Cycle 4 treatment. Imaging will include chest and abdomen. Bone Scans and Brain CT/MRI may be performed as clinically indicated. Scans do not have to be repeated once disease progression is documented.

**h:** Adverse events related to fulvestrant and/or everolimus/placebo will be followed for 30 days after the last dose of study therapy (fulvestrant and/or everolimus/placebo) or until ≤ grade 1 or if the grade is >1, the event must be permanent and stable. Please note- Serious adverse events >30 days after last dose of fulvestrant and/or everolimus/placebo are not reported unless the event may be related to everolimus/placebo.

**i:** CBC and chemistry may be used to assess ongoing toxicity but are not required in the Continuation Phase for patients who receive fulvestrant alone. Patients who continue fulvestrant with everolimus should periodically have CBC, chemistries, fasting glucose, fasting lipids, HBV DNA, HCV RNA-PCR per labeling guidelines.

**j:** Study Drug Compliance (Pill Diary) for those patients who receive everolimus in the Continuation Phase.

**k:** All patients including those that discontinue protocol therapy will be followed for 3 years from the time of randomization. Patients that have not progressed during the Induction or Continuation Phase will continue to have imaging scans completed every 12 weeks, +/- 1 week (every 3 months) until documented progression.

**l:** PFTs with DLCO as medically indicated only, (PFTs are not otherwise required during course of study).

**m:** Follow every 3 months for disease progression and survival. Initiation of any new systemic therapy will also be documented.

\* Day 1 of each cycle is defined as the day in which fulvestrant is given, including the first fulvestrant dose, third fulvestrant dose, and every dose thereafter (the second fulvestrant dose is given on day 15 of the first cycle only).

^ End of Induction/End of Treatment should be performed within 30 days of last dose of fulvestrant.

**f:** Continuation Phase: Patients in the Continuation Phase should continue to receive fulvestrant alone (if originally randomized to placebo) or in combination with everolimus (if originally randomized to everolimus) at the same dose and schedule (+/- 1 week window for scheduled therapy/tests/visits; delays due to holidays, weekends, bad weather or other unforeseen circumstances will be permitted) until disease progression or unacceptable toxicity.

